2 ELIGIBILITY ASSESSMENT AND ENROLLMENT

2.1 ELIGIBILITY CRITERIA

- 2.1.1 Inclusion Criteria
- 2.1.1.1 Age \geq 18 years, no upper age limit.
- 2.1.1.2 Patients diagnosed with a leukemia or lymphoma as follows:
 - Chronic or acute leukemia forms of HTLV-1 associated adult T-cell leukemia (see Appendix B);
 - Peripheral T-cell lymphoma (angioimmunoblastic, hepatosplenic, or not otherwise specified); or,
 - Cutaneous T-cell lymphoma stage III or IV with circulating monoclonal cells (B1 or B2) and/or erythrodermia (T4)
 - T-cell prolymphocytic leukemia (T-PLL)

NOTE: Diagnosis must be validated by the Pathology Department, NCI.

2.1.1.3 Patients must have measurable or evaluable disease.

NOTE: All patients with greater than 10% abnormal CD4+ homogeneous CD3^{low} strongly CD25+ expressing cells, or greater than 5% Sézary/T-PLL cells, among the PBMCs in the peripheral blood will be deemed to have evaluable disease.

- 2.1.1.4 Abnormal T cells must be CD52⁺ as assessed by flow cytometry or immunohistochemistry.
- 2.1.1.5 Patients must have a life expectancy of ≥ 2 months
- 2.1.1.6 Patients must have been refractory or relapsed following front-line therapy; those with CTCL or PTCL who have CD30⁺ disease must have progressed during or after treatment with brentuximab vedotin or are unable to receive treatment due to allergy or intolerance.
- 2.1.1.7 Patients must have recovered to less than grade 1 or to baseline from toxicity of prior chemotherapy or biologic therapy and must not have had major surgery, chemotherapy, radiation or biologic therapy within 2 weeks prior to beginning treatment. **NOTE:** Exceptions to this include events not considered to place the subject at unacceptable risk of participation in the opinion of the PI (e.g., alopecia).
- 2.1.1.8 DLCO/VA and FEV -1.0 > 50% of predicted on pulmonary function tests.
- 2.1.1.9 Adequate laboratory parameters, as follows:
 - Serum creatinine of ≤ 1.5 x the upper limit of normal
 - AST and ALT < 3 x the upper limit of normal
 - Absolute neutrophil count $\geq 1,500/\text{mm}^3$ and platelets $\geq 100,000/\text{mm}^3$

Version Date: 09/24/2021

- $2.1.1.10 \text{ ECOG} \leq 1 \text{ (see Appendix A)}.$
- 2.1.1.11 Patients must be able to understand and sign an Informed Consent Form.
- 2.1.1.12 All patients must use adequate contraception during participation in this trial and for 4 months following completing therapy.
- 2.1.2 Exclusion Criteria
- 2.1.2.1 Patients who have received any systemic corticosteroid therapy within 4 weeks prior to the start of therapy, or 12 weeks if given to treat graft versus host disease (GVHD), with the exception of physiological replacement doses of cortisone acetate or equivalent.
- 2.1.2.2 Patients who have undergone allogeneic stem cell transplantation and have required systemic treatment for GVHD (including but not limited to oral or parenteral corticosteroids, ibrutinib, and extracorporeal phototherapy) within the last 12 weeks
- 2.1.2.3 Clinical evidence of (parenchymal or meningeal) CNS involvement or metastasis. In subjects suspected of having CNS disease, a magnetic resonance imaging (MRI) scan of the brain and lumbar puncture should be done to confirm.
- 2.1.2.4 Documented HIV, active bacterial infections, active or chronic hepatitis B, hepatitis C.
 - Positive hepatitis B serology indicative of previous immunization (i.e., HBsAb positive and HBcAb negative) or a fully resolved acute hepatitis B infection is not an exclusion criterion.
 - If hepatitis C antibody test is positive, then the patient must be tested for the presence of HCV by RT-PCR and be HCV RNA negative.

NOTE: HIV-positive patients are excluded from the study. Alemtuzumab may produce a different pattern of toxicities in patients with HIV infection; in addition, the depletion of T cells produced by alemtuzumab may have adverse effects on HIV-positive individuals.

Version Date: 09/24/2021

- 2.1.2.5 Concurrent anticancer therapy (including other investigational agents).
- 2.1.2.6 History of severe asthma or presently on chronic inhaled corticosteroid medications (patients with a history of mild asthma not requiring corticosteroid therapy are eligible).
- 2.1.2.7 Patients with smoldering and lymphomatous ATL.
- 2.1.2.8 Pregnant or nursing patients.
- 2.1.2.9 Patients who have previously received alemtuzumab are ineligible. **NOTE:** Patients with relapsed T-PLL who have achieved at least a partial response to prior alemtuzumab are eligible.
- 2.1.2.10 Uncontrolled intercurrent illness including, but not limited to, ongoing or active infection, symptomatic congestive heart failure, unstable angina pectoris, cardiac arrhythmia, moderate/severe graft versus host disease, cognitive impairment, active substance abuse, or psychiatric illness/social situations that, in the view of the Investigator, would preclude safe treatment or the ability to give informed consent and limit compliance with study requirements.

2.1.3 Recruitment Strategies

Patient accrual will be facilitated by a contract with the University of the West Indies (Jamaica) that refers patients with ATL and from the population of patients screened in the lymphoid malignancy clinics of the National Institutes of Health. These will include both referrals from outside physicians as well as patient self-referrals. In addition, we participate in a locoregional consortium of eight academic institutions within the mid-Atlantic region that shares information regarding active clinical protocols and aims to enhance patient recruitment across the region. In addition, this study will be posted on NIH websites and NIH Social Media forums.

2.2 SCREENING EVALUATION

2.2.1 Screening activities performed after a consent for screening has been signed

Note: Screening evaluation testing/procedures are conducted under the separate screening protocol, 01-C-0129 (Eligibility Screening and Tissue Procurement for the NIH Intramural Research Program Clinical Protocols). Assessments performed at outside facilities or on another NIH protocol within the timeframes below may also be used to determine eligibility once a patient has signed the consent.

Screening evaluation must be performed within 28 days prior to study enrollment, except as indicated below.

- Diagnosis of leukemia/lymphoma confirmed by the Laboratory of Pathology, NCI. Pathological confirmation of diagnosis can be carried out on available slides from either primary screen or biopsy performed either at the Clinical Center or outside institutions (no time restriction).
- Flow cytometry to assess CD52 and 1) CD3^{low}CD4⁺ CD25^{hi} (for patients with ATL), or 2) CD4⁺ CCR4⁺ CD27⁺ (for patients with CTCL) in the peripheral blood cells and lymphocyte sets and subsets. Send one 10 mL lavender top tube to the Immunology Service of the Department of Laboratory Medicine. See Section **5.1** for additional collection times.
- Complete medical history and physical exam with documentation of sites of disease.

Version Date: 09/24/2021

- Documentation of ECOG Performance Score (see Appendix A).
- Vital signs (VS): heart rate, blood pressure, respiration, temperature and oxygen saturation (SO2) by transcutaneous pulse oximeter.
- PET scan of the torso and CT scan of the chest, abdomen, pelvis and neck or MRI if CT scan is not sufficient or contraindicated. Other imaging studies may be done to document disease as appropriate and at the direction of the PI.
- Complete blood count (CBC) with differential.
- Acute Care Panel (sodium, potassium, chloride, total CO2, glucose, creatinine, BUN) Hepatic Panel (alkaline phosphatase, ALT, AST, total and direct bilirubin), LDH and Mineral Panel (serum calcium, phosphorous, magnesium, albumin)
- Serum pregnancy test in women of childbearing potential.
- Hepatitis B Surface Antigen, Hepatitis B Surface Antibody, Hepatitis B Core Antibody, and Hepatitis C. HIV 1/2, and HTLV-1/2 serologies.
- EKG
- Pulmonary function tests with DLCO.
- Echocardiogram with measurement of left ventricular ejection fraction (LVEF).
- MRI scan of the brain and lumbar puncture for patients with neurological symptoms or signs.
- Skin biopsy of clinically suspicious lesions. One to three lesions may be biopsied if necessary to confirm the diagnosis of ATL or CTCL.

2.3 PARTICIPANT REGISTRATION AND STATUS UPDATE PROCEDURES

Registration and status updates (e.g., when a participant is taken off protocol therapy and when a participant is taken off-study) will take place per CCR SOP ADCR-2, CCR Participant Registration & Status Updates found here.

2.3.1 Treatment Assignment Procedures

2.3.1.1 Cohorts

Number	Name	Description
1	Leukemia or lymphoma	Patients with a T-cell leukemia or lymphoma (i.e., chronic or acute HTLV-1 associated ATL; peripheral T-cell lymphoma; cutaneous T-cell lymphoma; or, T-cell prolymphocytic leukemia [up to 30 patients])

2.3.1.2 Arms

Number	Name	Description
1A	Experimental: Dose Escalation	IL-15 for 10 doses over two weeks followed by alemtuzumab for 4 weeks per dosing schema to determine the maximum tolerated dose (MTD)
1B	Experimental: Dose Expansion	IL-15 for 10 doses over two weeks followed by alemtuzumab for 4 weeks at the maximum tolerated dose (MTD)

Version Date: 09/24/2021

2.3.1.3 Treatment Assignment

Treatment assignment is single arm, open-label, and non-randomized/non-stratified (i.e., subjects in Cohort 1 directly assigned to Arm 1 based on the dose level open to enrollment).

2.4 BASELINE EVALUATION

The following tests/procedures should be performed within 28 days prior to initiating treatment unless otherwise noted. It is not necessary to repeat test that were done for screening if they were done within 28 days prior to initiating treatment.

2.4.1 Clinical Evaluations

- Complete medical history and physical exam with documentation of sites of disease.
- Documentation of ECOG Performance Score (see **Appendix A**).
- Vital signs: heart rate, blood pressure, respiration, temperature and oxygen saturation (SO2) by transcutaneous pulse oximeter.
- Height and Weight

2.4.2 Laboratory Evaluations

- Serum pregnancy test in women of childbearing potential, repeated within 3 days prior to starting the study drug.
- Thyroid function tests
- Troponin
- Urinalysis
- CBC with differential and reticulocyte count
- Acute Care Panel (sodium, potassium, chloride, total CO2, glucose, creatinine, BUN)
 Hepatic Panel (alkaline phosphatase, ALT, AST, total and direct bilirubin), LDH and
 Mineral Panel (serum calcium, phosphorous, magnesium, albumin)
- Serum Lipase and Amylase
- Glucose-6 phosphate dehydrogenase (G-6PD)
- Antinuclear antibody (ANA), rheumatoid factor (RF) and anti-thyroid antibody
- CMV/EBV PCR; Quantitative, Blood
- HLA typing (A, B, C, DR, DQ)

2.4.3 Imaging Studies

Every participant should have an evaluation of known sites of disease as part of baseline evaluation. NOTE: Only results from NIH are accepted.

- One or more of the following studies: CT, MRI, FDG-PET and/or clinical photography
- Patients with neurological symptoms or signs should undergo MRI scan* of the brain and lumbar puncture

*NOTE: The MRIs to be done in this study may involve the use of the contrast agent gadolinium, if clinically indicated.

Version Date: 09/24/2021

2.4.4 Other Procedures

• Bone marrow biopsy and aspiration to assess for disease involvement (not needed if one has already been performed at the NIH Clinical Center within 1 year prior to enrollment).

- All patients with cutaneous disease will have their disease assessed by a dermatologist using the modified Severity Weighted Assessment Tool [Appendix I].
- Selected patients with cutaneous disease will have clinical photography performed to document their skin disease.

2.4.5 Research Correlates

See Section 5 for additional information.

3 STUDY IMPLEMENTATION

3.1 STUDY DESIGN

This is a single institution nonrandomized, IL-15 dose-escalation Phase I study evaluating the combination of s.c. rhIL-15 with alemtuzumab in patients with relapsed or refractory ATL, PTCL, T-PLL, or CTCL where both escalating doses of rhIL-15 and sequential administration of alemtuzumab will be administered.

rhIL-15 will be given as a subcutaneous (s.c.) injection once daily Monday-Friday for a total of 10 doses.

On Day 1 (or before if clinically indicated) of Week 3, patients will be admitted to the NIH Clinical Center inpatient unit for the alemtuzumab infusions. Patients may be discharged from the inpatient unit and treated in the outpatient clinic when their experience with the treatment indicates that the alemtuzumab can be given safely in an outpatient setting. **During week 3, all patients will receive standard initial (tachyphylaxis) dosing of alemtuzumab by 2-hour intravenous infusion:** Day $1 \rightarrow 3$ mg, Day $2 \rightarrow 10$ mg, and Day $3 \rightarrow 30$ mg and day $5 \rightarrow 30$ mg.

After completion of the initial dosing, alemtuzumab will be given to all dosing cohorts **during** weeks 4, 5 and 6 as the standard 30 mg on MWF schedule resulting in a total of 13 alemtuzumab treatments.

3.1.1 Dose-Limiting Toxicity for rhIL-15

There are some well-described, clinically inconsequential side effects associated with IL-15 immunotherapy that are addressed differently than with other types of cancer therapies and affect the consideration of DLTs. Patients receiving rh-cytokines often have an initial decrease in their total white blood cell (WBC) counts, significant lymphopenia and occasionally some degree of neutropenia early in the course of their treatment. Unlike cytopenias noted in patients receiving cytotoxic chemotherapies or alemtuzumab treatment, these drops are usually transient and presumed to be related to increased margination (adherence to blood vessel endothelium) or alterations in trafficking that reduces the number of circulating cells rather than the destruction of the mature effector and bone marrow precursor cells. As such, rh-cytokine treatment resulting in grade 3 or 4 cytopenia, especially lymphopenia, in the absence of signs of infection is not interpreted as a DLT.

DLT will be defined as follows:

Version Date: 09/24/2021

Any grade 3 or 4 toxicity possibly, probably or definitely related to the rhIL-15 treatment that occurs during the first 6 weeks of treatment, with the following exceptions:

Hematologic exceptions:

- Grade 3 or 4 lymphopenia
 - o rhIL-15 will be continued in the event of asymptomatic grade 3 or 4 lymphopenia, unless there are clinical signs of significant infection (persistent fevers, labile blood pressure, localized complaints or findings on physical exam, hypoxia or organ dysfunction).
- Grade 3 neutropenia
 - o rhIL-15 will be continued in the event of grade 3 neutropenia unless there are clinical signs indicating a significant infection, as listed above.
- Grade 3 leukocytosis (WBC > 100,000/mm³) in the absence of signs of leukostasis or other toxicities possibly related to the expansion of activated cells.
- Grade 3 or 4 anemia that lasts for \leq 3 days and does not cause hypotension or organ dysfunction. If the anemia last for more than 3 days, it is considered a DLT.

Other exceptions:

• Any event that can clearly be determined to be unrelated to the treatment regimen.

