3.1.2 Dose Escalation

Dose escalation will proceed in cohorts of 3 to 6 patients. Patients will not begin treatment at the next higher dose level until all patients treated at the previous dose level have completed the DLT evaluation window and an assessment of DLT has been completed.

Patients will receive s.c. rhIL-15 for the initial period Monday-Friday week 1 and 2. They will be assigned to a dose level sequentially based on their order of entry into the study. The starting dose will be 0.5 mcg/kg/dose and in the absence of dose-limiting toxicities dose escalation will proceed to evaluate dose levels of 1.0 and 2.0 mcg/kg/dose. This initial part of the treatment will be 14 days in length and will be followed by 4 weeks (13 treatments) of alemtuzumab. Only toxicities occurring in this 6-week period will be considered in determining dose escalation. Dose-limiting toxicities are defined in Section 3.1.1. Dose-escalation rules are indicated in the table in Section 3.1.2. As just noted, the first 6 weeks of rhIL-15 and alemtuzumab treatment will be considered in defining criteria for dose escalation and the maximum tolerated dose (MTD).

Dose escalation will proceed in cohorts of 3–6 patients. The MTD is the dose level at which no more than 1 of up to 6 patients experience DLT during the first 6 weeks of treatment, and the dose below that at which at least 2 (of \leq 6) patients have DLT as a result of the drug. If a patient did not experience DLT and did not finish treatment, he or she will not be evaluable for toxicity and will be replaced in the dose level. An additional 3 patients may be enrolled to compensate for inevaluable patients.

Dose escalation table:

Dose Escalation Schedule				
Dose Level	Dose of IND Agent*			

Version Date: 09/24/2021

Dose Escalation Schedule			
Level 1 0.5 mcg/kg/dose			
Level 2 1 mcg/kg/dose			
Level 3 2 mcg/kg/dose			
* Doses are stated as exact dose in units (e.g., mg/m², mcg/kg, etc.) rather than as a percentage.			

Dose-escalation rules:

Number of Patients with DLT at a Given Dose Level	Escalation Decision Rule			
0 out of 3	Enter up to 3 patients at the next dose level			
≥ 2	Dose escalation will be stopped. This dose level will be declared the maximally administered dose (highest dose administered). Up to three (3) additional patients will be entered at the next lowest dose level if only 3 patients were treated previously at that dose.			

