3.1.2.1 Stopping Rules

Acute ATL patients can have rapidly progressive disease or can have severe disease related metabolic or organ dysfunction that can be exacerbated by treatment with alemtuzumab and fatal events during salvage treatment do occur. If 2 out of the first 15 patients treated in this trial have fatal (grade 5) SAEs regardless of presumed relationship to rhIL-15, entry and all treatment in this protocol will be halted and the data reviewed to better understand the possible contribution of rhIL-15 to these events.

If a patient develops grade ≥3 venous thromboembolism (VTE) during or within four weeks of treatment and while on appropriate VTE prophylaxis, no additional patients will be accrued on the study. Patients already enrolled on the study who are still undergoing treatment will be notified of the event before their next planned alemtuzumab dose and will not receive further doses of alemtuzumab.

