6.3.1 Definitions

Evaluable for toxicity: All patients will be evaluable for toxicity from the time of their first treatment with IL-15.

Evaluable for objective response: Only those patients who have measurable disease present at baseline, have completed the 6 weeks of therapy, and have had their disease re-evaluated will be considered evaluable for response. These patients will have their response classified according to the definitions stated below.

Evaluable Non-Target Disease Response: Patients who have lesions present at baseline that are evaluable but do not meet the definitions of measurable disease, have completed the 6 weeks of therapy, and have had their disease re-evaluated will be considered evaluable for non-target disease. The response assessment is based on the presence, absence, or unequivocal progression of the lesions.

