7.4 NIH REQUIRED DATA AND SAFETY MONITORING PLAN

7.4.1 Principal Investigator/Research Team

The clinical research team will meet on a weekly basis when patients are being actively treated on the trial to discuss each patient. Decisions about dose level enrollment and dose escalation if applicable will be made based on the toxicity data from prior patients.

Version Date: 09/24/2021

All data will be collected in a timely manner and reviewed by the principal investigator or a lead associate investigator. Events meeting requirements for expedited reporting as described in section 7.2.1 will be submitted within the appropriate timelines.

The principal investigator will review adverse event and response data on each patient to ensure safety and data accuracy. The principal investigator will personally conduct or supervise the investigation and provide appropriate delegation of responsibilities to other members of the research staff.

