8.2 ASSESSMENT OF SAFETY EVENTS

AE information collected will include event description, date of onset, assessment of severity and relationship to study product and alternate etiology (if not related to study product), date of resolution of the event, seriousness and outcome. The assessment of severity and relationship to the study product will be done only by those with the training and authority to make a diagnosis and listed on the Form FDA 1572 as the site principal investigator or sub-investigator. AEs occurring during the collection and reporting period will be documented appropriately regardless of relationship. AEs will be followed through resolution.

SAEs will be:

- Assessed for severity and relationship to study product and alternate etiology (if not related to study product) by a licensed study physician listed on the Form FDA 1572 as the site principal investigator or sub-investigator.
- Recorded on the appropriate SAE report form, the medical record and captured in the clinical database.
- Followed through resolution by a licensed study physician listed on the Form FDA 1572 as the site principal investigator or sub-investigator.

For timeframe of recording adverse events, please refer to section **6.1.1**.

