10 STATISTICAL CONSIDERATIONS

The primary objective of this trial is to determine the safety, toxicity profile, DLT and MTD of rhIL-15 administered at escalating doses s.c. in combination with alemtuzumab. There are three planned dose levels (0.5, 1, and 2 mcg/kg/dose s.c.) and one dosing strategy (weeks 1 and 2 Monday-Friday). In week three all patients will receive alemtuzumab: 3 mg on day 1, 10 mg on day 2, 30 mg on day 3 and 30 mg on Day 5 of the study. The therapy with alemtuzumab will be continued on weeks 4, 5 and 6 on a 3 x weekly schedule at 30 mg for a total of 4 weeks (13 treatments) of alemtuzumab.

The determination of MTD follows the 3+3 design in which 3 to 6 patients will be enrolled in each combination of dose level. In the initial cohort (Cohort 1), at least 3 patients will be enrolled to receive 0.5 mcg/kg/dose of rhIL-15. In Cohort 2, patients will be enrolled to receive 1 mcg/kg/dose of rhIL-15; and in Cohort 3 patients will receive 2 mcg/kg/dose of IL-15.

The MTD will be based on the assessment of DLT during the first 6 weeks of treatment and will be defined as the dose level at which less than one-third of patients (0/3 or 0-1/6 patients) treated at that dose experience a DLT, with the next higher dose level demonstrating a one-third or greater number of patients (≥2/3 or ≥2/6 patients) having DLT. If a patient did not experience DLT and did not finish the 6 weeks of therapy, this patient will not be evaluable for determination of the MTD and will be replaced in the dose level. An additional 3 to 6 patients will be enrolled at the MTD or, if no severe or dose-limiting toxicities are encountered, the maximum administered dose of rhIL-15, so that a total of 9 patients will be treated at this dose to better characterize the clinical activity of rhIL-15 in this patient population. Accordingly, if all dose levels are evaluated (6 patients per dose level with 9 total patients at the MTD or maximum administered dose) a maximum of 21 evaluable patients will be enrolled. Similarly, if all dose levels are evaluated, the minimum number of evaluable patients required will be 15. An additional 9 patients may be enrolled to compensate for inevaluable patients; thus, bringing the maximum accrual ceiling to 30.

It is expected that accrual can be completed in 60 months.

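### An rhIL-15-related death with no earlier countable grade 3–4 toxicity falls outside the DLT count, because the definition stops at grade 4 and non-completers without a DLT are replaced

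*Combined protocol and SAP*

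**What the plan says.** - **Definition.** Section 3.1.1 sets the DLT as "Any grade 3 or 4 toxicity possibly, probably or definitely related to the rhIL-15 treatment that occurs during the first 6 weeks of treatment". It then lists haematologic exceptions and excludes events clearly unrelated to the regimen. Neither grade 5 nor death is mentioned.
- **Link to escalation.** Section 3.1.2 adopts that definition: "Dose-limiting toxicities are defined in Section 3.1.1". The escalation table and the MTD definition both run on the resulting count.
- **Replacement.** Section 3.1.2 states: "If a patient did not experience DLT and did not finish treatment, he or she will not be evaluable for toxicity and will be replaced". Section 10 repeats the rule for patients who do not complete the 6 weeks, saying that "this patient will not be evaluable for determination of the MTD and will be replaced in the dose level". Neither section makes an exception for death.
- **Fatal events.** Section 3.1.2.1 has a separate rule, which begins "If 2 out of the first 15 patients treated in this trial have fatal (grade 5) SAEs regardless of presumed relationship to rhIL-15". It then halts entry and treatment for a data review. Here the protocol names death as a grade of its own.
- **Evaluability elsewhere.** Section 6.3.1 says "All patients will be evaluable for toxicity from the time of their first" IL-15 treatment.
- **Team review.** Section 7.4.1 says "Decisions about dose level enrollment and dose escalation if applicable will be made based on the toxicity data from prior patients".

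**The concern.** Most phase I definitions read grade 3 or higher, so that death is plainly included. This one names two grades and stops, while the protocol elsewhere uses grade 5 as a distinct category. Someone who dies during treatment has also not completed it. If no DLT occurred before the death, the replacement sentence applies and the slot is refilled.

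The primary objective is safety and the MTD, and both are decided by the DLT count. If the gravest rhIL-15 toxicity can leave that count, the table may allow escalation where counting the death would require three more patients or a stop.

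**Working it through.** **1. Reproduce the plan's own table.** Under the Section 3.1.2 rule, escalation follows 0/3, or 1/3 and then 0 of 3 more. With true DLT rate p:

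P(escalate) = (1−p)³ + 3p(1−p)² × (1−p)³

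At p = 20%: 0.512 + 3(0.2)(0.64)(0.512) = 0.709.

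| p | 10% | 20% | 30% | 40% | 50% | 60% |
|---|---|---|---|---|---|---|
| Computed | .906 | .709 | .494 | .309 | .172 | .082 |
| Section 10 | .91 | .71 | .49 | .31 | .17 | .08 |

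All six agree. The table holds for toxicities that enter the count.

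**2. Trace a related death through the rules.**

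- A related, non-excepted grade 3–4 toxicity came first: that toxicity is a DLT, and the patient counts.
- No such toxicity came first (a sudden death, or one preceded only by excepted haematologic changes) and therapy was incomplete: no DLT under 3.1.1, so replaced under 3.1.2 and Section 10.
- As in the second case, but the death follows the last dose and is still inside the window: therapy is complete, so the patient is evaluable and scored as no DLT.

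The second and third cases are the gap.

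**3. Size, given one such death plus two event-free patients in the first three.** Let q be the DLT rate in later patients (assumed 10/20/30%) and s = 1−q, with no later deaths.

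- Replaced: the substitute is event-free (0/3, escalate), or has a DLT (1/3) and three more are event-free. P = s + q·s³.
- Counted: 1/3 already, so three more must be event-free. P = s³.

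| q | Replaced | Counted | Gap |
|---|---|---|---|
| 10% | 0.9 + 0.1(0.729) = 0.973 | 0.729 | 0.244 |
| 20% | 0.8 + 0.2(0.512) = 0.902 | 0.512 | 0.390 |
| 30% | 0.7 + 0.3(0.343) = 0.803 | 0.343 | 0.460 |

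**4. One DLT, one such death and one event-free patient.** Replaced: the substitute and then three more must all be event-free, s⁴ = 0.656/0.410/0.240. Counted: 2/3, so escalation stops and P = 0.

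**5. Does the two-death halt close the gap?** Let each later patient also die of any cause with assumed probability d, a second death triggering the halt, so that s = 1−q−d in the step 3 formulas.

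| d | Replaced (q = 10/20/30%) | Counted |
|---|---|---|
| 5% | 0.911/0.834/0.732 | 0.614/0.422/0.275 |
| 10% | 0.851/0.769/0.665 | 0.512/0.343/0.216 |

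Both columns fall. Across d = 0, 5 and 10% the gap stays between 0.24 and 0.46.

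**6. Where this applies.** Escalation is possible only from 0.5 and 1.0 mcg/kg. At 2.0 mcg/kg, the top level, only the MTD designation is affected.

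**The case against.** **Most fatal toxicities pass through grade 3 or 4.** This is the strongest point, and it stands. Section 3.1.1 turns on toxicity that occurs, and the replacement rule turns on what the patient experienced. Section 8.2 says "AE information collected will include event description, date of onset, assessment of severity and relationship to study product" without saying whether the pre-fatal grade is kept as a separate entry, but data capture does not govern the DLT rule. A reader might infer that every rhIL-15-related death escapes the count. The documents do not support that: a death preceded by a related, non-excepted grade 3–4 phase counts however it was recorded. With vital signs around each rhIL-15 dose and blood tests at least three times a week (Sections 3.4.1 and 3.4.4), such a phase would often be seen.

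**A related death would not go unexamined.** This also stands. Besides the weekly team review and the power to suspend (Section 13.1), SAEs go to the sponsor's safety office within 24 hours (8.3). Deaths within 30 days not due to progression go to the Clinical Director within one business day (7.3). The IND sponsor reports serious unexpected suspected reactions to FDA (8.6). A reader might infer that escalation would proceed unnoticed, or that only the study team stands in the way; neither follows. Still, none of these provisions makes the death a DLT or bars replacement, and one death does not trigger the halt.

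**Section 6.3.1 makes everyone evaluable for toxicity.** It conflicts with Section 3.1.2, but being evaluable does not add grade 5 to the definition.

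**The figures are conditional.** They are, and the documents give no rate for the triggering event. In the s.c. monotherapy trial (Section 1.2.4.5), the only DLT was at 3.0 mcg/kg/day and the only serious adverse event at 2.0. Neither was at a level from which this trial escalates. That does not settle the rate for the combination with alemtuzumab.

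**Conclusion.** The point holds as a narrow gap in the written rule. A death in the 6-week window, at least possibly related to rhIL-15 and with no earlier related and non-excepted grade 3–4 toxicity, is replaced or scored as no DLT. The existing safeguards mean it would be reviewed, but they leave the count unchanged.

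The wording is clear, so confidence in the gap is high. The effect on the trial is uncertain. Once such a death has occurred alongside two event-free patients at 0.5 or 1.0 mcg/kg, replacing it raises the chance of escalating by 0.24 to 0.46. This rests on assumed later DLT rates of 10–30%, with patients independent. It would be tempting to read these as the trial's operating characteristics. They are not: they condition on an event whose probability the documents do not give, and the Section 10 table itself is correct.

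The gap is worth closing because it concerns the worst outcome in a trial whose primary objective is safety.

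**What to change.** 1. In Section 3.1.1, define a DLT as toxicity of grade 3 or higher, naming grade 5 explicitly. Keep the present attribution standard, time window and exceptions.
2. In Sections 3.1.2 and 10, add that a patient who dies within the 6-week window from an event at least possibly related to rhIL-15 counts as having a DLT and is not replaced, whether or not therapy was complete.
3. Leave deaths due only to alemtuzumab or disease outside the DLT count, under the two-in-fifteen halt.

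The cost is a wording amendment to three sections. The trade-off is that escalation becomes less likely after such a death (0.73 rather than 0.97 in the step 3 scenario at a 10% later DLT rate), which is the intended effect.
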